3.0 PATIENT SELECTION

3.1 Inclusion Criteria

- $3.1.1 \text{ Age} \ge 18$
- 3.1.2 Diagnosis of AML according to WHO (World Health Organization) criteria except acute promyelocytic leukemia AND
- 3.1.3 Refractory AML defined as failure to achieve CR after 2 cycles of induction chemotherapy or persistence of > 40% bone marrow blasts after one cycle of chemotherapy induction $\underline{\mathbf{OR}}$
- 3.1.4 Relapsed AML defined as any evidence of disease recurrence after achieving a documented first or greater CR $\overline{\mathbf{OR}}$
- 3.1.5 Relapsed AML after stem cell transplantation. 90 days (since stem cell infusion) must have elapsed between transplant and emergence of recurrent AML**OR**
- 3.1.6 Newly diagnosed AML in a patient >65 years old not considered fit for standard 7+ 3 chemotherapy or who declines such therapy after discussion of therapeutic options available.

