Marrow aspirate only will be obtained after the first ten days (on days 10 or 11) of decitabine in the first cycle. At the end of the first cycle and third cycle or at the time of full peripheral blood count recovery, whichever comes first, a bone marrow aspirate and biopsy will also be obtained. Marrow may be obtained between days 22 and 26 of the 1st and 3rd cycles, and a marrow at time of withdrawal from study is recommended but is optional.

Number of Cycles.

If there is no overt progression of disease (defined as doubling of the peripheral blood blast count) after the first cycle, the patient will proceed on study and receive two more cycles. If after the third cycle there is evidence of a PR/CR or stable disease, the patient will remain on study for 3 more cycles. The maximum number of cycles that each patient may receive is six. As noted above, physicians may use maintenance decitabine, but this will be off protocol.

Long Term Follow Up

Patients will be followed for survival status every 6 months for up to 2 years after last date of treatment.

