7.0 MEASUREMENT OF EFFECT Responses will be assessed at the end of cycle 1 (for progression only) and cycle 3 and at study conclusion or patient withdrawal from study (See 8.2 below).

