7.1 Definitions

- 7.1.1 Complete remission: Normocellular marrow (>20%) with < 5% blasts and no extramedullary leukemia. Absence of dysplasia. Normal peripheral blood counts ANC>1000 and platelets > 100,000. Patients with these criteria and persistently abnormal cytogenetics will be judged as complete remission, but these aberrations will be noted.
- 7.1.2 Partial remission: Normocellular marrow (>20%) with 5-20% blasts and no extramedullary leukemia.
- 7.1.3 Treatment failure: failure to achieve CR or PR.
- 7.1.4 Stable disease: No change in percentage of marrow blasts.
- 7.1.5 Relapse: The reappearance of circulating blast cells of the malignant phenotype; > 5% blasts in the bone marrow not attributable to another cause; and/or, the development of extramedullary leukemia.
- 7.1.6 Hematologic recovery: ANC \geq 1500 for 3 consecutive days; non-transfused platelets \geq 100; no leukemic blasts in the peripheral blood.
- 7.1.7 Duration of remission/response: defined as the time from documented remission/response to the time of progression.
- 7.2 Confirmatory Measurement/Duration of Response
 - 7.2.1 A bone marrow biopsy and aspirate will be obtained after cycle 3 and after each cycle and at the end of study at which time determination of a PR or CR will be made.
 - 7.2.2 Duration of overall response

The duration of overall response is measured from the time measurement criteria are met for CR or PR until the first date that recurrent or progressive disease is objectively documented.

The duration of CR is measured from the time measurement criteria are first met for CR until the first date that recurrent disease is objectively documented. Note will be made of use of maintenance decitabine.

- 7.2.3 Progression-Free Survival PFS is defined as the duration of time from start of treatment to time of progression.
- 7.2.4 Response Review

All bone marrow biopsies and aspirates will be reviewed by a hematopathologist.

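### The end of a partial remission is not settled: the relapse marrow rule overlaps the PR range, section 7 gives no marrow criterion for progression, and PFS omits relapse and death

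*Combined protocol and SAP*

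**What the plan says.** All section numbers refer to the combined protocol and SAP.

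- **Overall response (7.2.2)** runs "from the time measurement criteria are met for CR or PR until the first date that recurrent or progressive disease is objectively documented". The same section ends the duration of CR at recurrent disease alone.
- **Partial remission (7.1.2)** is "Normocellular marrow (>20%) with 5-20% blasts and no extramedullary leukemia". It sets no condition on blood blasts.
- **Relapse (7.1.5)** has three alternative limbs: circulating malignant blasts reappear, extramedullary leukemia develops, or there are "> 5% blasts in the bone marrow not attributable to another cause". None of them is restricted to patients who reached CR.
- **Duration of remission/response (7.1.7)** is "defined as the time from documented remission/response to the time of progression".
- **PFS (7.2.3):** "PFS is defined as the duration of time from start of treatment to time of progression".
- **Progression** has no entry in section 7. The only stated criterion is in 4.1.1.1 (Number of Cycles), where patients continue if there is "no overt progression of disease (defined as doubling of the peripheral blood blast count) after the first cycle". Section 7.0 adds: "Responses will be assessed at the end of cycle 1 (for progression only) and cycle 3".
- **Eligibility (3.1.4)** has "Relapsed AML defined as any evidence of disease recurrence after achieving a documented first or greater CR".

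**The concern.** A response duration needs an end event that a responder does not already meet on the day the response starts. For PR the relapse entry fails this test if it is applied as worded, because its marrow threshold lies at the bottom of the PR range.

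If relapse is instead taken to follow CR only, the end of a PR seen in the marrow alone rests on progression, and section 7 does not say what marrow finding counts as progression. Two readers could then give the same patient different durations.

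Two related defects sit in the same section. The two definitions of response duration do not name the same end events. The endpoint called PFS names neither relapse nor death, so as written it is a time to progression. A patient who dies without documented progression, or who relapses from CR in the marrow alone, has no stated place in it.

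At stake is whether any reported duration or PFS figure can be reproduced.

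**Working it through.** The plan gives no figure on this point, so the check sets the definitions side by side.

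**1. Overlap of PR and relapse.** PR covers marrow blasts of 5% to 20% (7.1.2). The marrow limb of relapse is above 5% (7.1.5). In whole percentages:

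- PR values: 20 − 5 + 1 = 16.
- PR values above 5%: 20 − 6 + 1 = 15.
- Share: 15/16 = 0.94. Only a PR at exactly 5% escapes.

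This is a share of possible values, not of patients.

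**2. If recurrence follows CR only.** The overlap disappears. The other two limbs of 7.1.5 (blood blasts and extramedullary disease) could still end a PR without contradiction. A PR lost only in the marrow would have to end at progression, and the doubling rule in 4.1.1.1 is the only criterion stated. That rule is tied to the decision after cycle 1. It names no reference count and contains no marrow value. It also cannot be applied when no blasts circulate, since 2 × 0 = 0.

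**3. One constructed patient.** Assumptions: PR with 12% marrow blasts after cycle 3, 30% after cycle 6, any marrow in between at 20% or less, and no circulating blasts or extramedullary disease at any time. Cycles last 28 days, extendable to 30 (4.1.1.1).

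| Reading | Duration of response |
|---|---|
| Marrow limb of 7.1.5 applied to PR | 12% > 5%, so 0 days |
| PR ends when marrow blasts exceed 20% | 3 × 28 = 84 days (3 × 30 = 90) |
| Blood doubling as the only progression rule | no end date |

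The marrow may be taken on days 22 to 26 (6.0), which moves the middle figure by a few days. The contrast remains.

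**4. The two duration entries.** 7.1.7 ends at progression. 7.2.2 ends at recurrence or progression. For a CR that recurs, only 7.2.2 names the event.

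**5. What does not move.** The Arm A decision in section 11.0 uses response counts: at least 3 of 9, then at least 10 of 24. Exact binomial calculation gives early termination 0.601 and type I error 0.0485 at a 25% response rate, and power 0.805 at 50%. These match the stated 60%, .05 and 80%. No duration or PFS value enters them.

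**The case against.** The strongest reply is that nobody would record a PR as lasting zero days. 7.2.2 separates the two cases by ending CR at recurrence and overall response at recurrence or progression. The natural reading is recurrence after CR and progression after PR. The first limb of 7.1.5 speaks of blasts reappearing, 3.1.4 ties relapse to an earlier CR, and 7.2.2 does not use the word relapse at all. This stands. A reader might infer from the overlap that PRs will be reported with zero duration, but the documents do not support that as the intended practice.

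A second reply is that progression is not left wholly open. Stable disease (7.1.4) means no change in the marrow blast percentage, a marrow is taken at suspected progression (6.0), and a hematopathologist reviews all marrows (7.2.4). A rise from 12% to 30% would plainly not be stable, and the doubling rule describes overt progression for one treatment decision. This also stands in part. A reader might infer that such a PR can never end, but that requires treating the 4.1.1.1 rule as the only definition. What remains is that no marrow value is stated, so the date of progression is a matter of judgment.

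A third reply is that little depends on these endpoints. Objective 1.1 lists CR, CRp, PR, event-free survival and overall survival, but neither response duration nor PFS. Section 11.0 plans no analysis of either. This stands and sets the severity.

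**Conclusion.** The point holds as a minor one. Applied literally, the marrow limb of 7.1.5 ends any PR above 5% blasts on its first day. On the more plausible reading, the end of a PR seen only in the marrow depends on a progression rule without a marrow criterion. On either reading, 7.1.7 and 7.2.2 disagree, and 7.2.3 labels as PFS an endpoint in which death is not an event.

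The 15 of 16 figure measures the overlap of the definitions. The 0, 84 to 90 days and open-ended results come from one constructed patient. The documents do not allow an estimate of how many Arm A patients would be affected.

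A reader might infer that the efficacy conclusion of Arm A is in doubt. It is not: PR itself is defined, and the Simon rule counts responses without regard to how long they last. The effect is confined to descriptive reporting of response duration and PFS.

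**What to change.** Four wording changes:

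1. **7.1.5:** limit only the marrow limb, for example 'in a patient in CR, >5% marrow blasts'. Keep the return of circulating blasts after clearance, and new extramedullary leukemia, as end events for both CR and PR. 'After clearance' is needed because 7.1.2 does not require a PR patient's blood to be free of blasts.
2. **7.2.2:** add that a PR also ends when marrow blasts exceed 20%.
3. **7.1.7:** replace the text with a reference to 7.2.2.
4. **7.2.3:** end PFS at the first of progression, relapse or death from any cause.

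Leave 4.1.1.1 as a treatment-continuation rule.

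The cost is drafting only, with no new tests and no change to treatment. The limits should be stated openly:

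- The 20% bound is the protocol's own upper limit for PR, but using it to end a response is new. A rise from 19% to 21% would end a PR, and a rise from 6% to 20% would not.
- The date of loss is known only to the marrow schedule. 7.2.1 asks for a marrow after each cycle, 6.0 only after cycles 1 and 3 and at end of study, and 4.1.1.1 makes the withdrawal marrow optional. From cycle 3 to cycle 6 the gap is about 84 to 90 days, and longer if treatment is delayed.
- Follow-up after treatment records survival status only, so a PR still held at the last marrow would be censored there.
- For a patient who never responds, progression in PFS remains a clinical judgment unless the sponsor also chooses a criterion for that case.

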8.0 CORRELATIVE STUDIES

Assessment of eIF4E Expression—This will be done on all patients on pre-study marrow aspirate. Light density marrow cells will be processed, and western blotting performed to determine if the AML is eIF4E positive (increased 2 to 3 Xs above normal controls). Immunohistochemistry will also be carried out with eIF4E and DAPI to document initial nuclear localization by confocal microscopy. Having this information at study entry will allow determination of ribavirin effects on eIF4E localization at subsequent sampling points and will also help us determine if some non-M4/M5 cases express this and whether this might affect rapamycin response.

Documentation of mTOR inhibition

Assays will be performed to determine the feasibility of measuring whether the biologic endpoint of mTOR inhibition has been obtained in those receiving rapmycin and whether eIF4E has been inhibited in those receiving ribavirin.

To assess eIF4E, p70S6 kinase, and 4E-BP1 phosphorylation, leukemia blasts will be isolated via Ficoll-Hypaque density gradient centrifugation, lysed with buffer containing 50 nM Tris, pH 8.0, 120 mM Na CL, 0.5% Nonidet P-40, and protease inhibitor cocktail (Roche). The protein concentration of the lysate will be determined by using the Bradford method (Bio-rad, Hercules, CA). Equal amounts of protein will be separated on a 4%-20% Tris-Glycine gel (Invitrogen) and transferred to a BioTrace PVDF membrane. Blots will be probed with primary antibody to p70S6 kinase and to 4E-BP1 (Cell Signaling, Inc). After washing and incubation with secondary antibody, immunoreactive proteins will be visualized by using the ECL Plus detection system (Amersham Biosciences). Blasts will be sampled pre-study and after day 10-11 of the first cycle and at days 22-26 of the first and 3rd cycle. It is anticipated that the number of blasts may be diminished by the latter two samplings to the point where cell numbers may become limiting in the assay, but we will attempt to determine that this endpoint has been met in the whole light density marrow population. In those cases where aspirate is a dry tap, Western analysis will be performed on peripheral blood. Antibodies for these assays will be purchased from Cell Signaling.

If cell numbers and amounts of protein lysate allow, to assess AKT phosphorylation, leukemic blasts isolated and lysed as described above will be blotted and probed with primary antibody to Akt or phospho-AKT (Cell Signaling). After washing and incubating with secondary antibody, immunoreactive proteins were visualized by using the ECL Plus detection system (Amersham Biosciences). If cell numbers are limiting, Akt and Phospho-Akt as well as p70S6K can be detected with a flow cytometric assay. ^{23, 34}

Other Correlative Studies to Assess apoptosis, cell cycle, and Leukemia Stem Cell Phenotype

At days 0, 11, and 22-26 of the first cycle, at day 22-26 of the 3rd cycle, and at end of study, light density cells will be analyzed for cell cycle status, apoptosis, and expression of an AML progenitor/blast phenotype (CD34+, CD38-, CD123+) by FACS analysis. CFU-L assays will also be plated. Cells will also be injected into NSG mice to determine presence of an engraftable leukemia stem cell. In brief, approximately 10(6) light density marrow cells will be injected in sublethally irradiated NSG mice via tail vein in a final volume of 0.2mL of PBS with 0.5% FBS. After 6 to 8 weeks, animals will be sacrificed and bone marrow will be analyzed for the presence of human cells by evaluation of human CD45 and human CD33 by flow cytometry ^{35, 36}. Any remaining cells will be frozen for future molecular analysis of response and resistance markers.

Timing of Correlative Studies

Pre-study marrow

- a. Cells for in vitro testing (MTT or Alamar Blue assays, apoptosis, cell cycle, viability, and snap and viable freeze for future molecular analysis.)
- b. Western blots for p70S6K, 4EBP-1, Akt, and eIF4E expression (10⁷ cells) and eIF4E localization by confocal microscopy (both arms); Gli-1 expression by Western or PCR to determine if this might predict for resistance to ribavirin (Arm B only).
- c. CFU-L assay—10(6) cells
- d. NSG reconstituting assay -10(7) cells

Day 11 aspirate (cycle 1)

- a. Light density cells for apoptosis, cell cycle, and viability
- b. Western blots for p70S6K, 4EBP-1, Akt, and eIF4E and expression of downstream mediators; eIF4E localization by confocal microscopy
- c. CFU-L assay
- d. NSG reconstituting assay

Day 28 cycle 1 (same studies)

End of cycle 3 (same studies)

End of cycle 6 (same studies)

End of study marrow (recommended but optional) (same studies)

9.0 REGULATORY AND REPORTING REQUIREMENTS

Each patient will be monitored for side effects associated with treatment. The NCI Common Toxicity Criteria will be used to assess toxicity

(http://evs.nci.nih.gov/ftp1/CTCAE/CTCAE_4.03_2010-06-14_QuickReference_8.5x11.pdf). All supportive measures consistent with optimal patient care will be given.

9.1 Adverse Event Definitions

.

An adverse event is any untoward medical occurrence in a patient or clinical investigation subject administered an investigational product regardless of causality assessment. An adverse event can therefore be any unfavorable and unintended sign (including an abnormal laboratory finding), symptom, or disease temporally associated with the use of an investigational product,

ULEU-13049 31 Version date: 09Aug2017

whether or not related to the investigational product. An adverse event is unexpected when the specificity or severity is not consistent with the current Package Insert for commercial drug.

A serious adverse event (experience) or reaction is any untoward medical occurrence that at any dose: results in death, is a life-threatening adverse event, requires inpatient hospitalization or prolongation of existing hospitalization, results in persistent or significant disability/ incapacity, or a congenital abnormality. The definition of serious adverse event (experience) also includes important medical event. Medical and scientific judgment will be exercised in deciding whether expedited reporting is appropriate in other situations, such as important medical events that may not be immediately life-threatening or result in death or hospitalization but may jeopardize the patient or may require intervention to prevent one of the other outcomes listed in the definition above. These will also usually be considered serious. Examples of such events are intensive treatment in an emergency room or at home for allergic bronchospasm; blood dyscrasias or convulsions that do not result in hospitalization; or development of drug dependency or drug abuse

9.2 Adverse Event Reporting

All adverse events occurring after the patient is assigned to a treatment group are to be recorded in the study records. Medical conditions/diseases present before starting study drug are only considered adverse events if they worsen after treatment assignment.

9.3 Serious Adverse Event Recording

Fatal or life –threatening adverse events will be phoned to the Principal Investigator, the Cancer Center Data Safety Monitoring Committee Chairperson within 24 hours of notification.

Follow-up information may include hospital admission records, discharge summaries and autopsy reports, where applicable.

The Principal Investigator (PI) shall also make an accurate and adequate report to the reviewing Institutional Review Board (IRB) on any serious and unexpected AE.

9.4 Definition of Dose Limiting Toxicity and Determination of MTD

In arm B of the study, a dose limiting toxicity will be a grade 3 or 4 non-hematologic toxicity which is deemed probably or definitely due to study drug (ribavirin or combination of decitabine and ribavirin). As noted above, in this population of AML patients, Grade 3 infections, fatigue, weight loss, and electrolyte imbalances will be appropriately treated but are not deemed study related toxicities and will not result in dose modifications.

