4.1.1 Study schema

Note: Those patients with morphologic M4/M5 subtypes²⁸ will be treated on Arm B and all other subtypes on Arm A. At study entry, all patients will have samples procured for testing of eIF4E expression but this will not determine allocation to arm A or B which will be made solely on the basis of FAB subtype. M4 subtype is acute myelomonocytic leukemia and M5 acute monocytic leukemia.

- Decitabine (Arms A and B)
- 20mg/m2 will be given as an intravenous infusion daily for 10 consecutive days starting on day 1 of cycle 1.
- In subsequent cycles, decitabine will be given for 5 days (day 1-5)

Rapamycin (Arm A)

- o For non-M4/M5 AML cases²⁸
- A 6 mg loading dose will be administered on Day 11 in cycle 1 and day 6 in subsequent cycles. Thereafter, 2 mg/day will be administered per schedule below. This may be reduced to 1 mg/day if levels are elevated (>15 ng/mL).
- o Toxicities will be as defined in section 9 using NCI Common Toxicity Criteria for Adverse Events (CTCAE (version 4.0) Appendix 3)
- o Rapamycin will be given from day 11 to 22 in cycle 1 and on days 6 to 22 in subsequent cycles.

Dose Level	Rapamycin	Decitabine
Level -1	1 mg	20 mg/m2
Level 1	2 mg	20 mg/m2

The rapamycin dose for phase II of the study was chosen based on results from the phase I study (ULEU08049).

Ribavirin (Arm B)

For M4/M5 cases²⁸—These patient are anticipated to have high eIF4E expression as expressed by Western blotting²⁴.

In cycle 1, ribavirin will be dosed from Day 11 through Day 28.

In subsequent cycles, ribavirin will be started on Day 1 on a continuous basis until study completion. These doses were chosen based on those found effective and tolerated in previous studies²⁴.

Dose level cohorts are listed in the table below. Subject enrollment will start at **Dose Level 1** (1000 mg). Enrollment in subsequent dose levels (escalation to Dose level 2 and 3, or de-escalation to Level -1 and -2) will follow the dose escalation and dose de-escalation plans as outlined below.

ULEU-13049 14 Version date: 09Aug2017

Dose Level	Ribavirin	Decitabine	Description
Level -2	600 mg bid	20mg/m2	Dose de-escalation cohort
Level -1	800 mg bid	20mg/m2	Dose de-escalation cohort
Level 1	1000 mg bid	20mg/m2	Initial cohort
Level 2	1200 mg bid	20 mg/m2	Dose escalation cohort
Level 3	1400 mg bid	20mg/m2	Dose escalation cohort

Dose Escalation Plans for Ribavirin (Arm B)

Number of patients with DLT at a given dose level	Escalation Decision Rule

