0 out of 3	Enter 3 patients at the next dose level
≥ 2	Dose escalation will be stopped. This dose level will be declared the maximally administered dose (highest dose administered). Three (3) additional patients will be entered at the next lowest level if only 3 patients were treated previously at that dose.
1 out of 3	Enter at least 3 more patients at this dose level. – If 0 of these 3 patients experience DLT, proceed to the next dose level. -If 1 or more of this group suffer DLT, then dose escalation is stopped, and this dose is declared the maximally administered dose. Three (3) additional patients will be entered at the next lowest dose level if only 3 patients were treated previously at that dose.
≤ 1 out of 6 at highest dose level below the maximally administered dose	This is generally the recommended phase 2 dose. 6 patients must be entered at the recommended phase 2 dose before going to Phase 2.

An ad hoc confidential person will ensure that no unexpected adverse events have occurred at each dose level before enrollment on the next dose level commences. This will be handled through the DSMB of the James P Wilmot Cancer Center. THIS WILL REQUIRE THAT THE LAST PERSON ENROLLED AT THE PRIOR COHORT HAS BEEN FOLLOWED FOR 30 DAYS FROM THE START OF THERAPY.

Dose De-escalation: If 1000 mg bid proves to be the MTD, a cohort at 800 mg bid will be treated, and if that is too toxic, one at 600 mg bid will be enrolled (level -2). No further dose de-escalation would be planned. Safety assessment at each cohort would be as indicated above.

4.1.1.1

Cycle Duration

Cycles will begin on an every 28 day basis which may be extended to 30 days to account for weekends, holidays, logistics of marrow aspirate and biopsy scheduling.

Routine Clinical Monitoring.

Routine CBC with differential and platelets as well as a comprehensive metabolic profile including renal and hepatic function will be evaluated on a twice weekly basis and more frequently as cytopenias or metabolic abnormalities indicate. For those patients receiving rapamycin, a trough Rapamycin level will be performed at day 14 and 21 of each cycle.

Marrow Status Monitoring.

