9.5 Data and Safety Monitoring

Study Investigators will conduct continuous review of data and patient safety. The Investigator will submit quarterly progress reports of these data to the Clinical Trials Monitoring Committee for review. The review will include for each treatment arm/dose level: the number of patients enrolled, withdrawals, significant toxicities as described in the protocol, serious adverse events both expected and unexpected, dose adjustments, and responses observed. The PI

ULEU-13049 32 Version date: 09Aug2017

maintains a database of all adverse events with toxicity grade and information regarding treatment required complications, or sequelae. The Investigator will submit a copy of the AE spreadsheet along with the Progress Report to the Clinical Trials Monitoring Committee for review.

- Any serious adverse event that is serious, related AND unexpected must be reported within 10 calendar days to both the DSMC and the RSRB (see RSRB guidelines).
- Serious adverse events that are related AND expected or unrelated AND unexpected will be reported to the Committee for review at the quarterly meeting. SAE reports are expected to include sufficient detail so that the DSMC can determine the severity, toxicity grade, expectedness, treatment required, and a follow up report documenting resolution or if there are sequelae. Unless otherwise specified in the protocol, serious adverse events that require detailed reports (but not necessarily expedited) are expected, related, non-hematologic toxicities of grades 3, 4 or 5.

The Data Safety Monitoring Committee provides oversight of study progress and safety by review of accrual and events at regularly scheduled meetings. The frequency of review is determined by the size, risk and complexity of the trial, and is assigned by the Protocol Review Committee at the time of their initial review and approval. The Data and Safety Monitoring Committee will monitor all adverse event rates utilizing a cumulative spreadsheet listing of all events submitted along with progress reports by the PI. All serious adverse events that have occurred in the prior 3 months will be reviewed at the regular quarterly meeting of the DSMC in order to confirm toxicity grade, expectedness, relatedness, sequelae, follow up required, and risk to current or future subjects.

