The ribavirin dose escalation arm of this study will be a phase I dose escalation plan, so only tabular descriptions of toxicity and outcomes will be generated. The design of the phase I portion of the study is a standard 3+3 up and down design (See Section 7 for details). A minimum of 3 and a maximum of 6 patients will be entered at each dose level. The starting dose level as well as each subsequent dose increment (decrement) will be pre-specified. The first 3 patients will be treated at the starting dose level. If none of the 3 patients experiences dose-limiting toxicity, the dose will be escalated to the next higher level, and another 3 patients will be treated at the escalated level. However, if 1 of the first 3 patients experiences a dose-limiting toxicity, three more patients will be treated at the same dose level. The dose escalation continues until at least two patients among 3 or 6 patients experience toxicities, or until the highest prespecified dose level is reached. The MTD is defined as the highest dose level for which at least 5 of 6 subjects did not experience a DLT. Once the MTD has been established, the study will subsequently expand to a phase II study at the MTD level to obtain further safety and efficacy data. The Data Safety and Monitoring Board of the JP Wilmot Cancer Center will be utilized to review the data between cohorts and prior to escalating from phase I to a phase II portion of the study.

As noted in section 8, the correlative studies will be primarily exploratory. We will utilize a Chi square method to determine a correlation between clinical response and mTOR mediator inhibition as assessed by p70S6 kinase expression or 4EBP1 expression. Both response (yes/no) or decreased expression (yes/no) will be treated as binary variables, and decreased expression will be defined as at least a 25% decrease by densitometry or flow cytometric measurement. We will also determine the mean decrease in expression in the responding and non-responding groups for further descriptive correlations. In the treatment arm with ribavirin, similar analysis will be performed for eIF4E expression.

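### Two Arm B dose-finding phrases are wrong as written: a related death with no earlier grade 3–4 stage is not a DLT, and the de-escalation trigger names the tolerated dose

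*Combined protocol and SAP*

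**What the plan says.** **DLT definition.** Section 9.4 states for Arm B that "a dose limiting toxicity will be a grade 3 or 4 non-hematologic toxicity which is deemed probably or definitely due to study drug". It then sets aside grade 3 infections, fatigue, weight loss and electrolyte imbalances. Grade 5 is not mentioned. Section 9.5, on which serious events need detailed reports, does name it: "expected, related, non-hematologic toxicities of grades 3, 4 or 5".

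**How the count is used.** Section 11 says that "if 1 of the first 3 patients experiences a dose-limiting toxicity, three more patients will be treated at the same dose level". It defines the MTD as the highest level at which at least 5 of 6 patients had no DLT, and it carries that dose into the phase II expansion. A further sentence in section 11 ends escalation once two or more patients among 3 or 6 have toxicities; it uses neither the term DLT nor a grade.

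**De-escalation.** Section 4.1.1 says that enrollment at levels other than the starting one "will follow the dose escalation and dose de-escalation plans as outlined below". In the escalation table, the row for 2 or more DLTs reads "This dose level will be declared the maximally administered dose (highest dose administered", and adds: "Three (3) additional patients will be entered at the next lowest level if only 3 patients were treated previously at that dose". The fourth row takes as the usual recommended dose the highest level below the maximally administered dose with at most 1 DLT in 6, and requires six patients there. The separate de-escalation sentence reads "If 1000 mg bid proves to be the MTD, a cohort at 800 mg bid will be treated", and continues "and if that is too toxic, one at 600 mg bid will be enrolled (level -2".

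**The concern.** A 3+3 design is a counting rule. The number of patients with a DLT decides whether the next level opens, whether a level is filled to six, and which dose is expanded. The most serious related outcome should be in that count by rule, not by an unwritten correction. As worded, section 9.4 is not monotonic in severity: a related grade 4 infection is a DLT, because the exemption covers grade 3 only, but a related infection that is fatal without a recorded grade 3–4 stage is not.

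The de-escalation sentence has a different fault. It uses MTD for the dose that proved too toxic, while section 11 uses MTD for the dose that proved tolerable. Followed to the letter, it lowers the dose in the wrong case and stays silent in the right one.

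**Working it through.** The plan states no power or error rate for Arm B and gives no event rates, so there is no figure to reproduce and no probability to compute. The check applies the stated rules to specific outcomes.

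**Part (a): the count with and without grade 5.** Inputs: the DLT definition (9.4), the escalation table (4.1.1), and the 1-of-3 rule and MTD criterion (section 11). *Death* here means a related, non-hematologic fatal event with no earlier grade 3–4 stage. If the same toxicity was first grade 3 or 4 and not exempt, the patient already has a DLT under 9.4.

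| Outcome at one level | Count as written | Count if grade 5 is included |
|---|---|---|
| 1 death in the first 3 | 0/3: table opens the next level | 1/3: 3 more patients at the same level |
| 1 death + 1 grade 3–4 DLT in 6 | 1/6: 6 − 1 = 5 without DLT, MTD criterion met | 2/6: 6 − 2 = 4 without DLT, criterion not met |

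In the first row only one patient is affected, so section 11's two-patient sentence does not apply and the difference stands. In the second row two patients have toxicities, so that sentence stops escalation on either count. What remains open is whether the level itself qualifies as the MTD, because that criterion is written in DLTs.

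**Part (b): the de-escalation trigger.** Inputs: the starting level of 1000 mg bid, the table and the de-escalation sentence (4.1.1), and the MTD definition (section 11).

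| Outcome | Section 11 | Escalation table | De-escalation sentence, literally |
|---|---|---|---|
| 1000 mg bid: at most 1/6 DLTs; 1200 mg bid: 2 or more | MTD is 1000 mg bid | Recommended dose is 1000 mg bid | Opens 800 mg bid |
| 1000 mg bid: 2 or more DLTs | MTD is not 1000 mg bid | 1000 mg bid is the maximally administered dose | Not triggered |

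In the second case the row for 2 or more DLTs does not itself add patients at 800 mg bid. Its condition is that 3 were treated there before, and at the starting level that number is 0. The fourth row does point there: 800 mg bid is the highest level below the maximally administered dose, and six patients are needed at the recommended dose. The route down can therefore be inferred from the table, but the sentence written to trigger it contradicts the MTD definition in both cases.

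**The case against.** The strongest reply is that neither slip would mislead anyone running the trial, and that other text limits the damage. Most of this stands.

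- Many fatal toxicities pass through grade 3 or 4 and already count. This is right, and it confines part (a) to deaths with no such stage.
- A reader might infer that two related deaths in three patients would be scored 0/3 and the dose raised. The documents do not support that: section 11 stops escalation when two patients have toxicities, whatever the grade.
- Fatal events are phoned in within 24 hours (9.3). Review precedes each new level (4.1.1 and section 11), and serious events that are both related and unexpected get expedited review (9.5). These make an actual miss unlikely. None of them turns the death into a DLT, though, and the check in 4.1.1 is worded for unexpected events.
- A reader might also infer that the de-escalation sentence is the only way to reach 800 mg bid. It is not, given the fourth table row and the labelling of 800 and 600 mg bid as de-escalation cohorts.
- The intent of the sentence is plain from its continuation about 800 mg bid being too toxic. This is agreed; it makes the fault one of wording, not of design.

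The reply does not remove two things. The 1-of-3 rule and the MTD criterion still omit such a death, and no reading reconciles the de-escalation trigger with section 11.

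**Conclusion.** Both phrases are wrong as written, and the severity is minor. In part (a), the error is one patient in the DLT count for each related death without an earlier grade 3–4 stage. That is enough to change 1/3 to 0/3, or 2/6 to 1/6 at the MTD criterion. In part (b), the trigger is literally inverted, with the intended meaning recoverable from context. The conclusion rests on reading the stated rules literally and assumes no event rates. The documents do not say how often these cases would arise, so a claim that the chance of escalation is overstated by some amount would rest on invented rates. No sample size or error rate is affected.

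**What to change.** In section 9.4, define the DLT as a *grade 3, 4 or 5 non-hematologic toxicity*, keeping the attribution requirement and the grade 3 exemptions as they are. Deaths from AML do not become DLTs, because the event must still be probably or definitely attributed to study drug.

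In the de-escalation sentence of section 4.1.1, replace the condition that 1000 mg bid is the MTD with the condition that it *is declared the maximally administered dose (2 or more DLTs)*. This is the table's own term for the too-toxic dose and leaves MTD with its single meaning in section 11.

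The cost is two one-phrase edits in an amendment, with no change to sample size, dose levels or visits.
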